# 5.3. Lifestyle Considerations

#### 5.3.1. Meals and Dietary Restrictions

No dietary restrictions are required before or after dose administration.

#### 5.3.2. Caffeine, Alcohol, and Tobacco

Participants must abstain from ingesting caffeine- or xanthine-containing products (e.g., coffee, tea, cola drinks, and chocolate) for 48 hours prior and during quarantine and for 48 hours prior to all visits requiring spirometry.

Participants must not consume alcohol for 72 hours prior and during quarantine and for 72 hours prior to any study site visits.

Participants must not smoke or use tobacco or nicotine containing products for 72 hours prior to and during quarantine. Participants that are current smokers may be continued in the study if, in the opinion of the PI, cessation of smoking during quarantine will not lead to withdrawal symptoms which could interfere with the accurate recording on the symptom diary card.

## 5.3.3. Activity

Participants must refrain from strenuous exercise for 48 hours prior and during quarantine and for 48 hours prior to each study site visit (unless it is within the usual activity of the participant) in order to avoid potential spurious elevation of clinical laboratory safety parameters.

## 5.3.4. Other Restrictions

Participants will be instructed to avoid close contact with vulnerable people as described in Section 2.3.1.4 for two weeks after they leave the Quarantine Unit.

## 5.4. Screen Failures

Screen failures are defined as participants who sign the study specific ICF but are not subsequently enrolled into the study.

For individuals who do not meet the criteria for participation in this study (screen failure), the Investigator will decide whether the participant should be permanently excluded from the study or invited back for repeat assessments (i.e., repeat clinical laboratory test) if the initial screening assessments are still within the allowed screening windows or rescreening for a later quarantine, as appropriate.

# 6. Study Intervention

Study intervention is defined as any investigational intervention(s), marketed product(s), placebo, or medical device(s) intended to be administered to a study participant according to the study protocol.

Study interventions administered to participants are described in Table 2.

## 6.1. Study Interventions Administered

Participants will be inoculated with an Influenza A/California/2009 H1N1 virus on Day 0. Participants will receive an IV infusion with SAB-176 or placebo on Day 1.

Intervention Name	SAB-176	Placebo	Influenza A/California/ 2009 H1/N1 virus
Туре	Drug	Other	Virus
Dose Formulation	Purified hIgG in a sterile liquid formulated in 10 mM glutamic acid monosodium salt, 262 mM D-sorbitol, 0.05 mg/mL Tween 80, pH 5.5, administered as a liquid solution for injection in 0.9% sodium chloride	Sodium chloride 0.9% solution (normal saline)	Ampoule, Liquid
Unit Dose Strengths	Up to 50 mg/kg	Not applicable	The inoculum virus titre is determined in an infectivity assay, the titre is reported in tissue culture infectious dose (TCID 50 ) per mL (log 10 TCID 50 /mL). The challenge dose is approximately 3.5 x 10  log 10 TCID 50 .
Dosage Levels	A single dose up to 50 mg/kg	A single dose of 0 mg/kg	A single dose of virus will be delivered. Dose volume delivery method is provided in the AP.
Route of Administration	IV infusion	IV infusion	Intranasal
Use	Experimental	Placebo-comparator	Infectious challenge agent
IMP and Non-IMP	IMP	IMP (Placebo)	-
Challenge	-	-	Challenge virus

#### Table 2: Study Intervention

Intervention Name	SAB-176	Placebo	Influenza A/California/ 2009 H1/N1 virus
Sourcing	Sponsor	Provided centrally by HVIVO	Provided centrally by hVIVO
Packaging and Labelling	SAB-176 will be supplied in clear glass vials as a liquid purified hIgG in a sterile liquid formulated in 10 mM glutamic acid monosodium salt, with 262 mM D-sorbitol, and 0.05 mg/mL Tween 80, at a pH of 5.5. Each vial contains 74.17 mg / mL. The vials will be labeled and packaged in an outer vial box. Packs of up to 15 vials/boxes will be packaged together for ease of shipment/storage	Placebo (normal saline) will be supplied by the study site	Virus Challenge Inoculum will be provided in vials. The details of the virus challenge agent packaging and labelling will be provided in the AP
Current/Former Name or Alias	SAB 176	n/a	n/a

# 6.2. Preparation/Handling/Storage/Accountability

## 6.2.1. Interventional Product / Placebo

SAB-176 is diluted in normal (0.9%) sterile saline under aseptic conditions. The diluted product is intended for administration by the IV route. The dose of IMP will be calculated. The pharmacy will prepare a bag containing the dose of SAB-176 plus as much normal (0.9%) saline as is needed to reach the concentrations for the study. The infusion of SAB-176 (active treatment) or normal saline control (placebo) will be provided in an opaque bag to obscure the bag (as SAB-176 may develop bubbles like IVIg if agitated). The drip chamber will also be covered, but accessible if needed by nursing staff for verification of flow rate, etc. The infusion will continue at a stable rate of up to 2.0 mL/min. Further details can be found in the Investigator's Brochure.

Participants randomised to the control (placebo) infusion will receive normal (0.9%) saline in approximately the same volume as they would have received if randomized to the active arm.

hVIVO will receive supplies of investigational product / placebo after it has had Qualified Person sign off by the Good Manufacturing Practice (GMP) Pharmacy provider and it has been verified ready for dispatch by the unblinded Study Monitor. All investigational product / placebo supplies will be used only for this protocol and for no other purpose.

Ready-to-dispense investigational product / placebo will be supplied by the pharmacy for each quarantine prior dosing. Once received at hVIVO, hVIVO will perform stock level accountability and the investigational product / placebo will be stored at 15 to 25°C securely. Investigational product / placebo accountability will be controlled by hVIVO and monitored by the Study Monitor throughout the study and at study close-out.

The Investigator will ensure that all supplies are received by a responsible person, all deliveries and returns are documented and signed for, and the condition of the investigational product / placebo is monitored. Accurate records will be kept of when and how much investigational product / placebo is dispensed and used in the study. Any reasons for departure from the protocol dispensing regimen will be recorded.

Accountability records will be available for verification by the Study Monitor at each monitoring visit. At the completion of the study, there will be a final reconciliation of all investigational product / placebo.

## 6.2.2. Challenge Virus

Challenge virus inoculum will be prepared according to the hVIVO AP and administered in accordance with hVIVO's standard operating procedures (SOPs). Each participant will be allocated a unique vial containing the Challenge virus and will receive the inoculum intranasally.

The Challenge virus stock, Influenza A/California/2009 H1N1, was manufactured under current GMP. The Challenge virus stock has undergone quality testing performed during manufacturing (identity, appearance, sterility, infectivity, and contaminants) according to pre-determined specifications, and has subsequently also passed an extensive panel of adventitious agent testing. The Challenge virus is stored in a secure -80°C freezer (normal temperature range -60°C to -90°C).

The time from the Challenge virus inoculum thawing to inoculation should be no longer than 4 hours. All administrations will be made by a member of the clinical team and witnessed by a second member of the team. The exact time of inoculation will be recorded in the administration log. Accurate records will be kept of when and how much study inoculum is prepared and used. The oversight process will be signed off prior to administration of the Challenge virus. Any non-compliance or problems with the inoculation will be recorded in the participant's source notes and reported to the PI.

#### 6.2.3. All Study Interventions

- 1. The Investigator or designee must confirm appropriate temperature conditions have been maintained during transit for all study intervention received and any discrepancies are reported and resolved before use of the study intervention.
- 2. Only participants enrolled in the study may receive study intervention and only authorised study site staff may supply or administer study intervention. All study intervention must be stored in a secure, environmentally controlled, and monitored (manual or automated) area in accordance with the labelled storage conditions with access limited to the Investigator and authorised study site staff.
- 3. The Investigator, institution, or the head of the medical institution (where applicable) is responsible for study intervention accountability, reconciliation, and record maintenance (i.e., receipt, reconciliation, and final disposition records)
- 4. Further guidance and information for the final disposition of unused study interventions are provided in the Study Reference Manual or other specified location.

## 6.3. Randomisation and Blinding

hVIVO assigns a unique 6 digits number to each participant in the hVIVO database. This number will be used to identify a participant up to the point of randomisation, on source documents, on all study

correspondence and in the study database. A separate randomisation number will be allocated to the participants at randomisation and will be used for allocation of study intervention (SAB-176 or placebo).

A computer-generated randomisation schedule will be generated using SAS. Once assigned, that randomisation number shall not be reassigned.

Randomisation numbers will follow a 3-digit format e.g., [001]. A copy of the randomisation code list will be sent to the unblinded pharmacist preparing the study intervention, so that study intervention (SAB-176 or placebo) can be prepared for each participant as appropriate. The randomisation number encodes the participant's assignment to receive SAB-176 or placebo in a 1:1 ratio.

Each participant will be dispensed blinded study intervention, labelled with his/her unique randomisation number, throughout the study. With the exception of the unblinded pharmacist, the unblinded person preparing the randomisation code list, the unblinded Clinical Research Associate and the Quality Assurance auditors where necessary, the Investigator and all other clinical and non-clinical staff, (including the Study Statistician, data management staff), and the participants will remain blinded to the treatment allocation until after the database has been locked and approval for study unblinding has been given.

Following database lock, on receipt of authorisation from the Sponsor, a copy of the randomisation code list will be provided to the Study Statistician to conduct study unblinding prior to analysis.

Participants who are replaced as per Section 7.4 will be replaced and assigned a new, unique randomisation number equalling the randomisation number of the replaced participant, plus 100. This will ensure that the replacement participant receives the same allocated blinded study intervention as the participant who is being replaced.

An individual access to a secured website will be provided to the Investigator. The website, compliant with 21CFR part 11 guidelines, will be used if unblinding is required. In case of an emergency, the Investigator has the sole responsibility for determining if unblinding of a participant's study intervention assignment is warranted. Participant safety must always be the first consideration in making such a determination. If the Investigator decides that unblinding is warranted, the Investigator should make a reasonable attempt to contact the Sponsor prior to unblinding a participant's intervention assignment, provided that this would not delay emergency treatment of the participant. When the Investigator breaks the code, they will have to indicate on the website the reason for unblinding. The person who carried out the unblinding and the date and time of code breaking will be automatically recorded. After confirmation of the code break, the treatment allocation will appear on the screen. A notification with the treatment allocation will also be provided by email. A notification, without the treatment allocation, will be provided to the study team. Furthermore, the Sponsor must be notified within 24 hours after breaking the blind. Once the study is complete, the unblinded database will be provided to the Sponsor.

Even if the code is broken, blood samples for safety will continue to be drawn for the remainder of the planned study period following the last dose as long as doing so will not compromise participant welfare.

The study intervention must be discontinued after unblinding, but the participant will be followed up until resolution of any AEs.

## 6.4. Study Intervention Compliance

When participants are dosed at the study site, they will receive study intervention and Challenge virus directly from the Investigator or designee, under medical supervision. The date and time of each dose

administered at the study site will be recorded in the source documents and recorded in the case report form (CRF). The dose of study intervention and study participant identification will be confirmed at the time of dosing by a member of the study site staff other than the person administering the study intervention.

Any non-compliance or problems with the administration of the study intervention will be recorded in the participant's source notes and reported to the Sponsor if appropriate.

# 6.5. Concomitant Therapy

Any medications taken and changes in medications from the time the participant signing the study specific ICF, up to final study contact Day 28 (±3 days), will be recorded in the source data. Any medication (including over-the-counter or prescription medicines, vitamins, and/or herbal supplements) or other specific categories of interest that the participant is receiving at the time of enrolment or receives during the quarantine/outpatient stage will be stored, prescribed and administered in line with their label-specific requirements, and recorded according to the parameters required by the clinical database.

Participants will be reminded to refrain from using any over-the-counter medication without the approval of the Investigator and must notify the study site as soon as possible if they are prescribed any medication. All medications must be stopped prior to the planned date of viral challenge unless in the opinion of the Investigator and/or Sponsor's Medical Expert (SME), the medication will not interfere with the study procedures or compromise participant safety.

Medications prohibited throughout the study are shown in Table 3.

Prohibited medication	Washout
Systemic (oral and parenteral) antiviral drugs.	4 weeks prior to first study visit.
Influenza vaccine	6 months prior to first study visit.
Use or anticipated use during conduct of the study of concomitant medications (prescription and non- prescription), including vitamins or herbal and dietary supplements within the specified windows, unless in the opinion of the Investigator the medication will not interfere with the study procedures or compromise participant safety.	
 
Within 7 days prior to the planned date of viral challenge:
 
Herbal supplements
 
Any medication or product (prescription or over the counter) for symptoms of nasal congestion
 
Short and long-acting antihistamines.
 
Within 21 days prior to the planned date of viral challenge:
 
Chronically used medications, vitamins, or dietary supplements, including any medication known to be moderate/potent inducers or inhibitors of cytochrome P450 (CYP) enzyme.
 

Any IMP used in another trial	Within 3 months (or 5 half-lives of the IMP used in the other trial), whichever is greater, prior to the planned date of viral challenge.

Any concomitant medication required for the participant's welfare may be given by the Investigator. However, it is the responsibility of the Investigator to ensure that details regarding the medication and the reason for its use are recorded appropriately in the source notes to permit their transfer to the clinical database.

The use of paracetamol and/or other allowed medications is permissible up to 7 days before the date of viral challenge. During the study periods, the Investigator may permit a limited amount of paracetamol (no more than 4 g per day i.e., maximum daily dose) or topical medication, as clinically required for the treatment of headache or any other pain. Other medication to treat AEs may be prescribed if required.

Medications which are permitted throughout the study are shown in Table 4.

#### **Table 4: Permitted Medication**

Permitted medication	Time period
Paracetamol	Maximum 4 g daily during the study period at PI discretion.
Oral contraceptives	Allowed at any time during the study.
Prescription and non-prescription medications, including vitamins or herbal and dietary supplements, not listed in prohibited medications are subject to approval by the PI.	

## 6.6. Dose Modification

Not applicable.

# 7. Discontinuation of Study Intervention/Withdrawal

## 7.1. Participant Withdrawal

A participant may withdraw his/her consent to participate in the study at any time, for any reason, without prejudice to his/her future medical care. Participants may decline to give a reason for their withdrawal. Additionally, the PI may withdraw a participant if, in their clinical judgement, it is in the best interest of the participant or if the participant cannot comply with the protocol. Wherever possible, the tests and evaluations listed for the Early Withdrawal visit should be carried out, and if clinically indicated, the participant should be invited back for a final follow up visit.

The Sponsor should be notified of all study withdrawals in a timely manner, and in cases where the withdrawal is due to a medical reason the participant would be referred to his/her GP.

Participants will be counselled that early withdrawal from the viral challenge phase of the study is strongly discouraged, as it may pose a risk both to the participant and his/her contacts. In the event of a participant insisting on early withdrawal during the challenge isolation period, the participant will be encouraged to stay and would be advised of the potential risks of carrying Influenza A/California/2009 H1N1 virus infection into the community, and to vulnerable groups in particular as described in Section 2.3.1.4.

If the participant withdraws consent for disclosure of future information, the Sponsor may retain and continue to use any data collected before such a withdrawal of consent.

If a participant withdraws from the study, he/she may request destruction of any samples taken and not tested, and the Investigator must document this in the site study records.

# 7.2. Participant Discontinuation

Participants will be withdrawn from study intervention for the reasons listed below. These participants must not receive any additional intervention but should continue to be followed for safety and immunogenicity. Additional unscheduled visits may be performed for safety reasons.

- Non-compliance with the study requirements and restrictions.
- Clinically significant abnormal laboratory findings, which in the opinion of the Investigator(s) and/or Sponsor, precludes further participation in the study.
- Development of inter-current illness which, in the opinion of the Investigator would compromise the health of the participant or the study objectives.
- The Investigator's decision that withdrawal from further participation would be in the participant's best interest.
- Termination of the study at the discretion of the Investigator(s) or Sponsor for safety, behavioural, or administrative reasons.
- The wish of the participant.
- Any intervention related SAEs.
- Anaphylactic reaction following dosing.
- The participant becomes pregnant.

Participants who are withdrawn from the study, will be requested to attend an Early Withdrawal Visit, with assessments as detailed in the SoA (Section 1.2).

## 7.2.1. Temporary Discontinuation / Temporary Delay in Enrolment

At the first study visit if a participant is found to be ineligible due to transient circumstances (such as acute disease and/or fever), dosing with IMP or inoculation will be postponed until the transient circumstances have been resolved and the participant will be re-invited to a later quarantine group within the allowed time window. For participant rescreening refer to Section 5.4.

## 7.3. Lost to Follow up

A participant will be considered lost to follow-up if he or she repeatedly fails to return for scheduled visits and is unable to be contacted by the study site.

The following actions must be taken if a participant fails to return to the study site for a required study visit:

- The study site must attempt to contact the participant and reschedule the missed visit as soon as possible and counsel the participant on the importance of maintaining the assigned visit schedule and ascertain whether or not the participant wishes to and/or should continue in the study.
- Before a participant is deemed lost to follow up, the Investigator or designee must make every effort to regain contact with the participant (where possible, 3 telephone calls and, if necessary, a follow-up letter to the participant's last known mailing address or local equivalent methods). These contact attempts should be documented in the participant's medical record.
- Should the participant continue to be unreachable, he/she will be considered to have withdrawn from the study.

Discontinuation of specific sites or of the study as a whole are handled as part of Appendix 1.

# 7.4. Participant Replacement Strategy

Participants may be replaced in this study.

If a participant discontinues from study intervention OR withdraws from the study a replacement participant may be enrolled if deemed appropriate by the Investigator and Sponsor. The replacement participant will generally receive the same allocated blinded study intervention as the participant being replaced. The replacement participant will be assigned a new unique randomization number.

## 7.5. Stopping Rules

The PI and the SME will perform safety reviews on available clinical and virology data as appropriate during the quarantine period.

Three clinical scenarios relating to the incidence of SAEs/suspected unexpected adverse reactions (SUSARs) during the study and the procedures that should be performed in each case are presented in the Table 5 below:

#### Table 5: Study Stopping Rules

Status	Criterion	Procedure
1	A report has been received of one (or more) SUSAR(s) in any, one (or more) participant(s).	If such a status occurs at any point during the study, then further administration of SAB-176 will not take place. The PI and the SME will review the data and make decisions on whether it is appropriate to recommence dosing (approval of a substantial amendment from the competent authorities is required) or terminate the study.
2	No SUSAR have been reported but an overall pattern of clinical changes or symptoms exists, attributed to the IMP, which may appear minor or moderate in terms of individual AEs, but which collectively represent a concern for safety.	If such a status occurs at any point during the study, then further administration of IMP will not take place. The PI and the SME will review the data and decide on whether it is appropriate to recommence dosing (approval of a substantial amendment from the competent authorities is required) or terminate the study.
3	Unexpected virus-related SAE or unexpected virus-related AEs of clinical concern have been reported following HVC. *Expectedness will be assessed by referring to the Challenge virus dossier.	If such a status occurs at any point during the study, then the PI and the SME will review the data and decide based on expectedness* of the viral event. If the event is unexpected, further administration of the virus will not take place. The PI and the SME will review the data and decide on whether it is appropriate to recommence inoculation (approval of a substantial amendment from the competent authorities is required) or terminate the study.

In any event, participant follow-up should continue until resolution or stabilisation of AEs and final follow-up on Day 28 (±3 days).

Further enrolment into the study may be either temporarily or permanently discontinued if:

- An unacceptable number of severe or life-threatening exacerbations take place (as determined by the PI).
- If two or more (or a group of participants) experience clinically significant life-threatening AEs that are deemed to be significant by the PI.

Development of a group or cluster of clinically significant AEs that represent a safety risk to participants that are deemed to be significant by the PI.

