## 8. Study Assessments and Procedures

Unless otherwise stated, study assessments will be performed according to hVIVO SOPs.

Study procedures and their timing are summarised in the SoA (Section 1.2). Protocol waivers or exemptions are not allowed. Adherence to the study design requirements, including those specified in the SoA, is essential and required for study conduct. Immediate safety concerns should be discussed with the Sponsor upon occurrence or awareness to determine if the participant should continue or discontinue study intervention.

All screening evaluations must be completed and reviewed to confirm that potential participants meet all eligibility criteria. The Investigator will maintain a screening log to record details of all participants screened and to document eligibility or record the reasons for screening failure, as applicable.

For all study assessments, the nearest value obtained prior to dosing will be used as the baseline measure for assessments, unless stated otherwise.

Procedures conducted as part of the hVIVO Generic Screening process and obtained before signing of the study specific ICF may be utilised for screening or baseline purposes provided the procedures met the protocol-specified criteria and were performed within the time frame defined in the SoA.

Where applicable, unless otherwise stated, normal ranges will be identified in the Investigator Trial Master File (TMF).

• The maximum amount of blood collected from each participant over the duration of the study, including any extra assessments that may be required, will not exceed 550 mL for any given 8-week period. Repeat or unscheduled samples may be taken for safety reasons or for technical issues with the samples.

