#### **10.1.5.** Committees Structure

This study will not include an early safety data review. However, participant safety will be continuously monitored by the Sponsor's internal/external safety review committee which includes safety signal detection at any time during the study.

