#### 10.1.9. Study Discontinuation

The Sponsor reserves the right to temporarily suspend or discontinue the study for any reason at any time. In addition, the study may be stopped at any time if, in the opinion of the PI, the safety data suggest that the medical safety of participants is being compromised.

If the study is suspended or terminated for safety reason(s), the Sponsor will promptly inform the PI, and will also inform the regulatory authorities of the suspension or termination of the study and the reason(s) for the action.

The Pl/Investigator is responsible for promptly informing the REC and providing the reason(s) for the suspension or termination of the study.

If the study is prematurely terminated, all study data must be returned to the **Sponsor**. In addition, the study site must conduct final disposition of all unused IMPs in accordance with **the Sponsor**'s procedures for the study.

Termination of the clinical trial may also be initiated by the MHRA or the REC.

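### Challenge-safety endpoints count from inoculation on Day 0, but the set used for every safety analysis most naturally leaves out anyone not infused on Day 1

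*Combined protocol and SAP*

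**What the plan says.** - **Sequence.** Section 4.1 and the SoA place inoculation on Day 0 and the infusion of SAB-176 or placebo on Day 1.
- **Endpoints.** Section 3 lists three secondary endpoints for the safety of the challenge model: challenge-related unsolicited AEs, challenge-related SAEs, and concomitant medication use. All run from inoculation to the Day 28 follow-up.
- **Sets.** In 9.3 the Safety Analysis Set needs randomisation plus one or more doses of study intervention, and people are analysed by what they received. The Enrolled population is everyone who consented, was eligible and was inoculated.
- **Assignment.** Section 9.4.7 puts every safety analysis on the Safety Analysis Set and tabulates AEs by treatment group. No safety analysis is assigned to the Enrolled population.
- **Routes to being inoculated but not infused.** Section 7.2 withdraws participants from study intervention for, among other reasons, intercurrent illness, significant laboratory findings or their own wish. Table 5 halts dosing after IMP events. Status 1 (a SUSAR) reads "If such a status occurs at any point during the study, then further administration of SAB-176 will not take place", and Status 2 (a worrying AE pattern attributed to the IMP) reads "then further administration of IMP will not take place".
- **Inoculation.** Only Status 3, for virus-related events, names the virus: "If the event is unexpected, further administration of the virus will not take place".

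**The concern.** The window for the challenge-safety endpoints opens about a day before the event that admits a participant to the set on which they are analysed. Someone who receives the virus and then, for whatever reason, does not receive the infusion has been fully exposed to the challenge. That person nevertheless has no clear place in the table meant to describe the safety of the challenge.

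The omission could be informative. If a participant is withdrawn before dosing on health or laboratory grounds, the reason may itself be an early consequence of inoculation, and the summary would then miss the kind of event it exists to show. Omission caused by a Table 5 dosing halt is different: it follows from somebody else's event and says nothing about the undosed participant's own health.

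At stake is the completeness of a secondary safety description in healthy volunteers. Neither the primary efficacy analysis nor the SAB-176 safety comparison is affected.

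**Working it through.** **Step 1: what study intervention means.** Three places use the term for SAB-176 or placebo only:
- the ITT row of 9.3 adds SAB-176 or placebo in brackets;
- 6.3 does the same when describing allocation;
- 6.4 names study intervention and challenge virus as two separate things.

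Pointing the other way, Section 6 refers to Table 2 for the interventions given, and Table 2 includes a column for the virus. The narrow meaning is the more natural one, but the usage is mixed.

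**Step 2: where a randomised, inoculated but uninfused participant falls.**

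| Set (9.3) | Narrow reading | Wider reading |
|---|---|---|
| Enrolled | in | in |
| Randomised | in | in |
| ITT (names SAB-176 or placebo) | out | out |
| Per Protocol (subset of ITT) | out | out |
| Safety | out | in, but with no treatment group |

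On the wider reading the participant enters the Safety Analysis Set. That set is analysed by intervention received, and 9.4.7 tabulates AEs by treatment group. A person who received neither SAB-176 nor placebo has no column. On either reading the plan does not place them in the challenge-safety table.

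**Step 3: illustration of size.** The plan gives no figure on this point to reproduce. Inputs: 60 inoculated (9.2), and the Wilson score interval, the default for proportions in 9.4.2.1. Assumptions: k of the 60 go undosed, with k = 1, 3 or 5, and one of those k has the trial's only challenge-related SAE. The documents give no value for k.

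Wilson limits = [x + z²/2 ± z·√(x(n − x)/n + z²/4)] / (n + z²), with z = 1.96 and z² = 3.8416.

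- Enrolled, 1/60 = 1.67%: centre = (1 + 1.9208)/63.8416 = 0.0458; half-width = (1.96/63.8416) × √(59/60 + 0.9604) = 0.0307 × 1.3942 = 0.0428. Limits 0.3% to 8.9%.
- Safety Analysis Set with x = 0: the lower limit is 0 and the upper limit reduces to z²/(n + z²).

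| k undosed | Share of 60 left out | Enrolled | Safety Analysis Set | Upper limit |
|---|---|---|---|---|
| 1 | 1.7% | 1/60 | 0/59 | 3.8416/62.8416 = 6.1% |
| 3 | 5.0% | 1/60 | 0/57 | 3.8416/60.8416 = 6.3% |
| 5 | 8.3% | 1/60 | 0/55 | 3.8416/58.8416 = 6.5% |

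The intervals overlap heavily, so precision is not the issue. What changes is whether the event appears in the table. With k = 0 the two populations coincide.

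**Step 4: who a paused inoculation could protect.** Members of a quarantine group share one Day 0 (10.6.1), so a pause cannot help those already inoculated. There is more than one group, since doses "will be supplied by the pharmacy for each quarantine prior dosing". A clinical phase of about 15 weeks less about 5 weeks per participant leaves Day 0s spread over up to about 10 weeks. Only later groups, and replacements under 7.4, could benefit.

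**The case against.** **The SAP may settle it.** Section 9.4 is a summary, and 9.3 lets the SAP add sets. That is true, and no separate SAP text is available to check. But 9.4.7 as written assigns every safety analysis to one set, and a possible later document does not change the stated rule.

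**Nothing is lost.** AEs are collected from consent (8.18.1), SAEs are reported individually within 24 hours (10.3.10), and 9.4.3.1 counts those receiving virus, those receiving SAB-176 or placebo, and withdrawals by reason. This stands, and it limits the point to the endpoint summary. Disposition counts do not, however, report challenge-related events.

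**Bias.** A reader might infer that people with early challenge events are especially likely to go undosed, so that the summary is biased. The documents do not show this. They give no count of undosed participants and no reasons for non-dosing in the gap of about a day. Sections 8.7 and 10.3.6.2 treat ordinary challenge symptoms as expected. Section 7.2 makes informative omission possible and no more.

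**Table 5.** A reader might also infer that inoculation could continue after a SUSAR, because Statuses 1 and 2 do not name the virus. The documents do not support that. Those rows leave two outcomes: recommencing dosing after an approved amendment, or termination. Section 8 bars waivers and says "Adherence to the study design requirements, including those specified in the SoA, is essential and required for study conduct", and the SoA puts the infusion on Day 1, so inoculating someone who cannot be infused would breach the design. There are discretionary stops as well: "Further enrolment into the study may be either temporarily or permanently discontinued if" heads a list of PI-judged criteria, and 10.1.9 says "The Sponsor reserves the right to temporarily suspend or discontinue the study for any reason at any time". Although 10.1.5 says "This study will not include an early safety data review", it provides for continuous monitoring by the Sponsor's safety review committee. What remains is a matter of wording.

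**Conclusion.** The point holds as a modest reporting gap. As written, the challenge-model safety endpoints are analysed on a set that most naturally excludes anyone inoculated but not infused; on the wider reading, such participants are included without a treatment group.

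The size cannot be determined from the documents and is zero if everyone inoculated is infused. In the illustration, a single challenge-related SAE is either 1/60 (1.7%, 0.3 to 8.9%) or absent from the table (0/59, upper limit 6.1%). That rests on the assumptions that at least one participant goes undosed and that the event falls on that participant. The conclusion about membership rests on the narrow meaning of study intervention and on no SAP provision overriding 9.4.7.

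The change is worth making because it is nearly free. The absence of the virus from Statuses 1 and 2 of Table 5 is a drafting matter only.

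**What to change.** Add to 9.4.7: *Challenge-related AEs and SAEs, and concomitant medications, from Day 0 are summarised on the Enrolled (all inoculated) population, with participants who did not receive SAB-176 or placebo shown separately.* SAB-176 safety stays on the Safety Analysis Set.

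The Enrolled population is already defined in 9.3 and the data are already collected, so no procedure is added. The cost is one sentence and one more summary table. If no protocol amendment is otherwise planned, the same sentence can go in the SAP before unblinding; 9.4.1 allows changes to the statistical plan to be described and justified there.

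Optional wording note: Statuses 1 and 2 of Table 5 could add that challenge inoculation is also paused while blinded dosing (SAB-176 or placebo) is halted. This records what the SoA and Section 8 already imply, and it would protect later quarantine groups and replacements only. The clinical threshold for stopping remains the sponsor's decision.
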